9.4.3 Pharmacokinetic Endpoints

PK blood samples will be collected as outlined in the SoA (Section 1.3). Lenvatinib concentration versus time data will be tabulated, summarized, and graphically presented.

Lenvatinib data will be pooled with available data from other studies and subjected to population PK analysis. The PK model will be parameterized in terms of clearance and volume of distribution. Details of the population PK analysis, if performed, will be provided in a separate analysis plan.

9.4.4 Palatability and Acceptability Questionnaire

Measurement of palatability will be assessed using a facial hedonic scale [Guinard, J. X. 2001] in participants receiving the suspension formulation in the study.

9.5 Analysis Populations

9.5.1 Efficacy Analysis Population

The EAS population will serve as the primary population for the analysis of antitumor activity data within each tumor type in this study. EAS is defined as all evaluable participants, who have measurable disease present at baseline and at least 1 postbaseline efficacy assessment, unless they have discontinued prior to the first efficacy assessment due to progressive disease. Details on the approach to handling missing data are provided in [Table 5](#).

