In the single-agent expansion cohort of patients with osteosarcoma treated at the RP2D of lenvatinib (n = 31), TEAEs occurred in 29 patients (93.5%). The most frequently reported TEAEs (occurring in 40% or more of subjects), in descending order of frequency were decreased appetite, headache, vomiting, hypothyroidism, and proteinuria. Grade ≥3 TEAEs were reported in 20 subjects (64.5%), and such events in >2 subjects were back pain and tumor pain. Twenty-eight subjects (90.3%) had TEAEs reported by the investigator to be treatment-related, which were Grade ≥3 in 7 subjects (22.6%). The most frequently reported treatment-related TEAEs, occurring in 30% or more of subjects, were decreased appetite, hypertension, and hypothyroidism. Four subjects (12.9%) had Grade 5 AEs during treatment: cardio-respiratory arrest (n = 2) and respiratory failure or respiratory distress (1 each). All were considered by the investigator to be secondary to disease progression and not related to study drug. Non-fatal SAEs occurred in 20 subjects (64.5%). Events that occurred in >1 participant each were: back pain (n = 4), pneumothorax (n = 4), dyspnea (n = 3), tumor pain (n = 3), and platelet count decreased (n = 2). Additionally, there were no treatment-related fatal TEAEs.

In the single-agent expansion cohort of 31 patients with osteosarcoma, PFS at 4 months (PFS-4m) was 37.8% (95% CI: 20.0, 55.4) and median PFS was 3 months (95% CI: 1.8, 5.4). The median follow-up time for PFS was 16.6 months (95% CI: 5.5, 16.6). Thirty of the 31 patients enrolled in this cohort had measurable disease per RECIST 1.1. Two subjects had a BOR of PR (6.7%; 95% CI: 0.8, 22.1), and an additional 13 subjects had SD ≥7 weeks (43.3%). The median duration of objective response was 4.6 months (95% CI: NE, NE). Additionally, one participant had evaluable disease with a BOR of non-CR/non-PD.

Overall, the toxicity profile observed for single-agent lenvatinib in pediatric patients with refractory/relapsed solid tumors in the dose-finding cohort is consistent with the lenvatinib toxicity profile observed in adults.

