5.5 Participant Replacement Strategy

A participant who is not evaluable for objective response will be replaced.

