8.2.1.2 Tumor Imaging During the Study

The first on-study imaging assessment should be performed the end of Week 8 \pm 7 days. Subsequent tumor imaging should be performed every 8 weeks until Week 24, then every 12 weeks (\pm 7days) thereafter during treatment (or sooner if there is evidence of PD). Imaging timing should follow calendar days from C1D1, and should not be adjusted for delays in cycle starts. Imaging should continue to be performed until disease progression is identified by the investigator, the start of new anticancer treatment, pregnancy, withdrawal of consent, or death, whichever occurs first.

Objective response should be confirmed by a repeat imaging assessment. Tumor imaging to confirm PR or CR should be performed at least 4 weeks after the first indication of a response is observed. Participants will then return to regular scheduled imaging, starting with the next scheduled imaging time point. Participants who receive additional imaging for confirmation do not need to undergo the next scheduled tumor imaging if it is less than 4 weeks later; tumor imaging may resume at the subsequent scheduled imaging time point.

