9.4.1 Efficacy Endpoints

Primary Endpoints

- **ORR:** defined as the proportion of participants with a confirmed (≥ 4 weeks after initial response) CR or PR per RECIST 1.1 or RANO for HGG as assessed by investigator, at Week 16.

Secondary Endpoints

- **ORR.**
- **BOR:** defined as the participant's best confirmed response (CR or PR) over the treatment period.
- **DOR:** defined as the time from the date of the first documented CR or PR to the date of the disease progression objectively documented or death (whichever occurs first).
- **DCR:** defined as the percentage of participants who have a BOR of CR, PR, or SD. To be assigned a best overall response of SD, the time from the first administration of study drug until the date of documented SD should be ≥ 7 weeks.
- **CBR:** defined as the percentage of participants who have a BOR of CR, PR, or durable SD (SD duration ≥ 23 weeks since the first dose of the study treatment).
- **PFS:** defined as the time from the date of the first administration of study drug until the date of first documentation of PD per RECIST 1.1 or RANO for HGG or death (whichever occurs first).

Tertiary/Exploratory Endpoints

- **OS:** defined as the time from the date of the first administration of study drug until the date of death from any cause.

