9.6 Statistical Methods

9.6.1 Statistical Methods for Efficacy Analyses

This section describes the statistical methods that address the primary and secondary efficacy objectives. Methods related to exploratory objectives will be described in the sSAP.

Antitumor activity data will be analyzed by each tumor type. The data cutoff for the primary study analysis for a given tumor type will be determined by the study team, based on the review of data at each interim analysis and predetermined futility guidance.

Only those participants who have measurable disease present at baseline and have their disease re-evaluated at postbaseline visits will be considered evaluable for ORR. These participants will have their response classified according to RECIST 1.1 or RANO for participants with HGG.

Primary Efficacy Analysis

ORR: Objective responses will count only confirmed CR and PR at Week 16. Estimated ORR and its exact 95% CI using the method of Clopper and Pearson will be presented.

Secondary Efficacy Analyses

The BOR will be provided with the descriptive statistics. The ORR, DCR, and CBR will be provided with exact 95% CIs using the method of Clopper and Pearson, and the DOR will be analyzed for responders using Kaplan-Meier approach.

The secondary endpoint of PFS will be analyzed using Kaplan-Meier product-limit estimates. Median PFS and the cumulative probability of PFS at 4, 6, 12, and 24 months will be presented with 2-sided, 95% CIs when an adequate number of at-risk participants at those time points warrant the estimate. The cumulative PFS probabilities will be plotted over time as appropriate.

A summary of the primary analysis strategy for the key efficacy endpoints is provided in [Table 5](#).

Table 5 Table Analysis Strategy for Key Efficacy Variables

Endpoint/Variable	Statistical Method	Analysis Population	Missing Data Approach
Primary Analyses – Within tumor type			
ORR (RECIST 1.1 or RANO for HGG) at Week 16	Summary statistics using Clopper and Pearson method	EAS	Participants in EAS with missing data are considered nonresponders.
Secondary Analyses – Within tumor type			
ORR	Summary statistics using Clopper and Pearson method	EAS	Participants in EAS with missing data are considered nonresponders.
BOR	Summary statistics using Clopper and Pearson method	EAS	Missing observation in EAS population are counted as nonresponders.

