DCR	Summary statistics using Clopper and Pearson method	EAS	Missing observation in EAS population are counted as nonresponders.
CBR	Summary statistics using Clopper and Pearson method	EAS	Missing observation in EAS population are counted as nonresponders.
DOR	Summary statistics using Kaplan-Meier method	All responders in EAS	Nonresponders are excluded in analysis.
PFS (RECIST 1.1 or RANO for HGG)	Summary statistics using Kaplan-Meier method	EAS	Censored at last assessment.
Abbreviations: BOR=best overall response; CBR=clinical benefit rate; DCR = disease control rate; DOR = duration of response; EAS = evaluable analysis set; ORR=overall response rate; PFS = progression-free survival; RANO= Response Assessment in Neuro-Oncology; RECIST 1.1 = Response Evaluation Criteria in Solid Tumors Version 1.1.			

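### PFS is analysed in the response-evaluable set, so a death before any postbaseline assessment that is not recorded as a stop for progression is left out, although it is a PFS event by definition

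*Combined protocol and SAP*

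**What the plan says.** The endpoint and its analysis set are defined in different places.

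- **Endpoint.** In Section 9.4.1 the PFS clock starts with the first dose. Its end is given as: "until the date of first documentation of PD per RECIST 1.1 or RANO for HGG or death (whichever occurs first". Sections 1.1 and 3 agree.
- **Method.** Section 9.6.1: "The secondary endpoint of PFS will be analyzed using Kaplan-Meier product-limit estimates", with the median and the probabilities at 4, 6, 12 and 24 months.
- **Population.** Section 9.5.1: "The EAS population will serve as the primary population for the analysis of antitumor activity data within each tumor type in this study". The PFS row of Table 5 names the EAS, and its missing-data entry is "Censored at last assessment".
- **Entry to the EAS.** Section 9.5.1 asks for measurable disease at baseline and "at least 1 postbaseline efficacy assessment, unless they have discontinued prior to the first efficacy assessment due to progressive disease". That exception is the only one, and death is not named in it.
- **Timing.** Section 8.2.1.2: "The first on-study imaging assessment should be performed the end of Week 8", with a window of 7 days either way.
- **Replacement.** Section 5.5: "A participant who is not evaluable for objective response will be replaced".

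The Safety Analysis Set (Section 9.5.2), which is everyone given at least one dose, is not used for any efficacy endpoint. No all-treated or sensitivity analysis of PFS is described.

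**The concern.** Evaluability belongs to response: without a second assessment, change in tumor size cannot be classified. It is not needed for a time-to-event endpoint that starts at first dose and includes death. There, a participant who dies unassessed supplies an observed event, and one who is alive and unassessed can be censored.

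The EAS rule removes the first kind of participant if the stop was not recorded as progression. Every death lost this way is an early event, so each loss can only raise the Kaplan-Meier curve. At stake are the reported median PFS and the PFS probabilities, in cohorts small enough for one participant to be visible.

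**Working it through.** **Step 1: who is lost.** Take a treated participant with measurable disease at baseline who dies in Week 5 without a postbaseline assessment.

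| Recorded course | In EAS? | PFS event by Section 9.4.1? |
|---|---|---|
| Stopped for progression, then died | Yes, by the exception | Yes |
| Died or stopped for another reason, never assessed | No | Yes |

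The second row is the gap. Section 7.1 lists objective progression separately from lack of clinical benefit in the investigator's opinion and from unacceptable toxicity, so a stop short of recorded progression is a real category.

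**Step 2: inputs for size.** The plan gives no PFS assumption and no count of such deaths. Sections 9.7.2 and 9.9 are redacted, but nothing here depends on them. As assumptions I use two figures from the osteosarcoma cohort in Section 2.2.1.2: 4-month PFS of 9/28 = 32.1% (reproduced) and median 3.0 months. The EAS sizes are n = 17 (the cap) and n = 9 (the minimum). The number of omitted deaths, k, is assumed to be 1 to 3.

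**Step 3: formulas.** With all k deaths before time t and no earlier censoring,

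S_all(t) = S_EAS(t) × n/(n + k).

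For the median, take an exponential EAS curve, S_EAS(t) = 0.5^(t/3.0). Setting S_all = 0.5 gives

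median_all = 3.0 × [1 − log2((n + k)/n)].

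**Step 4: results.**

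| n | k | 4-month PFS, all treated | Overstated by (points) | Median, all treated (months) | Overstated by (months) |
|---|---|---|---|---|---|
| 17 | 1 | 30.3% | 1.8 | 2.75 | 0.25 |
| 17 | 2 | 28.7% | 3.4 | 2.52 | 0.48 |
| 17 | 3 | 27.3% | 4.8 | 2.30 | 0.70 |
| 9 | 1 | 28.9% | 3.2 | 2.54 | 0.46 |
| 9 | 2 | 26.3% | 5.8 | 2.13 | 0.87 |
| 9 | 3 | 24.1% | 8.0 | 1.75 | 1.25 |

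Example: 32.1% × 17/18 = 30.3%. With k = 0 nothing changes.

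The two columns are separate illustrations. An exponential curve with median 3.0 months has 4-month PFS 0.5^(4/3) = 39.7%, not 32.1%. Section 2.2.1.2 also prints 37.8% for 4-month PFS in all 31 patients. Starting there, one omitted death costs 37.8% × 1/18 = 2.1 points at n = 17 and 37.8% × 1/10 = 3.8 points at n = 9.

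**Step 5: how large k might be.** Section 2.2.1.2 reports that "Four subjects (12.9%) had Grade 5 AEs during treatment" (4/31 = 12.9%, reproduced). It adds that the investigator attributed all four to progression, and it does not say when they occurred. As a guide to unassessed deaths not recorded as progression, 12.9% is at most a ceiling. Three deaths at n = 17 are 3/20 = 15.0% of those treated, and two at n = 9 are 2/11 = 18.2%. Both exceed that ceiling, so the lower rows of each block are the less likely ones.

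**The case against.** The strongest reply is that few participants will fall into the gap.

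- A death from progression may well be recorded as a stop for progression, which keeps the participant in the EAS.
- Section 8.2.1.3 calls for imaging at treatment discontinuation, within 4 weeks either way, unless a scan was done in the preceding 4 weeks. A participant who stops early for toxicity is therefore due a scan that would bring them in. A reader might infer that early toxicity stops are generally lost. The documents do not support that: it takes a missed scan, or death before it.
- Sections 4.1 and 8.2.1.2 allow imaging earlier than Week 8 when clinically indicated or when progression is suspected.
- In HGG, Appendix 8 lets tumor-related clinical deterioration count as progression without radiological change.

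These points stand, and they limit frequency. They do not give a PFS event to a participant who dies unassessed and is coded otherwise.

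It is also fair to say that sampling error is far larger: 5/17 = 29.4% has an exact 95% interval of 10.3% to 56.0%. But that interval does not reflect an error that always runs in one direction.

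Three further inferences go too far. The 12.9% figure does not predict the share lost, given the attribution and missing timing. Replacement is not what biases PFS: leaving out the event does that, whether or not someone else is enrolled. Nor do expansion and futility decisions move through PFS, because Section 4.1 bases them on objective response at Week 16.

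**Conclusion.** The mismatch is in the text: the endpoint counts death from first dose, while the analysis set can exclude a participant who has died. The direction is certain if any such death occurs, and there is no bias if none does. The number is unknown.

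Under the stated assumptions, one omitted death overstates 4-month PFS by about 2 points at n = 17 and 3 points at n = 9. Three would overstate it by about 5 and 8 points. The smaller size may be the relevant one for EWS and HGG, which Sections 1.1 and 4.4 say were not expanded. These figures assume osteosarcoma-like PFS, no censoring before 4 months and, for the median, an exponential curve.

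The plan should be changed, because the rule gives a wrong result whenever it applies and the correction is cheap. The effect is confined to a secondary, descriptive endpoint.

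**What to change.** In Table 5, change the PFS population from the EAS to the existing Safety Analysis Set, by tumor type, and add a sentence to Section 9.5.1 saying so. State these rules for participants with no postbaseline assessment:

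- Death before the first postbaseline assessment is an event at the date of death.
- Censor at Day 1 those who are alive, those who started new anticancer therapy before death, and those who died after a prespecified gap (for example, two missed scheduled assessments). Without the last two, a participant never scanned who dies many months later would be credited with a long PFS.

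Keep EAS-based PFS as supportive, and keep the EAS for ORR, BOR, DCR and CBR.

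The cost is one table cell and a few sentences. Survival status and subsequent anticancer therapy are already collected (Sections 1.3, 8.11.5.2 and 8.11.5.3). Participants censored at Day 1 add almost no information, and reported PFS may be slightly less favourable.

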9.5.2 Safety Analysis Population

The Safety Analysis Set population will be used for the analysis of safety data in this study. The safety analysis set population is defined as all participants who received at least 1 dose of the study drug.

At least 1 laboratory or vital sign measurement obtained after at least 1 dose of study treatment is required for inclusion in the analysis of each specific parameter. To assess change from baseline, a baseline measurement at C1D1 prior to allocation is also required.

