Cycle Day		1	8	15	1	15	1	1	1	At DC	30 days after last dose	Q8W for 24 weeks, then Q12W	Q12W	
Scheduling Window	-28 to -1		±2	±2	±2	±2	±2	±2	±2		±7	±7	±7	
INR or PT	X													INR or PT should only be performed as part of the screening assessment and as clinically indicated.
Urine Dipstick (or urinalysis) Testing	X	X		X	X	X	X	X	X	X	X			Dipstick is the preferred method for urinalysis. Urine dipstick/urinalysis testing can be performed within 7 days prior to the first dose of lenvatinib (C1D1) as part of the screening visit and does not need to be repeated at C1D1 (unless clinically indicated) and within 72 hours prior to the visit at subsequent cycles. Urine dipstick/urinalysis testing will be performed during screening, at C1D1, C1D15, C2D1, C2D15, and D1 of every subsequent cycle, or more frequently as clinically indicated, at the EOT and at the Safety FU visit. For participants with proteinuria ≥2+ (≥100 mg/dL), urine dipstick/urinalysis testing should be performed on D15 (or more

Study Period	Screening	Intervention Cycle = 28 Days					EOT	Post-treatment Visits			NOTES			
		1		2		3		4	5 – last	Safety FU		Efficacy (Imaging) FU Visits	Survival FU	
Cycle Day		1	8	15	1	15	1	1	1	At DC	30 days after last dose	Q8W for 24 weeks, then Q12W	Q12W	
Scheduling Window	-28 to -1		±2	±2	±2	±2	±2	±2	±2		±7	±7	±7	
														frequently as clinically indicated) until the results have been 1+ or negative for 2 treatment cycles. If a new event of proteinuria ≥2+ (≥100 mg/dL) occurs, refer to Section 6.6.3 for further management guidelines. Urine glucose should be performed as part of the urine dipstick/urinalysis.
TSH, Free T4	X				X			X	X ^a	X	X			The screening blood sample for thyroid function testing can be obtained within 7 days prior to the first dose of lenvatinib (C1D1) as part of the screening visit and does not need to be repeated at C1D1 (unless clinically indicated) and within 72 hours prior to the visit at subsequent cycles. TSH and free T4 should be assessed for all participants. Assessment should be obtained at screening C2D1, ^a every 2 cycles thereafter, at EOT and at the Safety FU visit. If not done locally, can be done at a central laboratory.

Study Period	Screening	Intervention Cycle = 28 Days					EOT	Post-treatment Visits			NOTES		
		1		2		3		4	5 – last	Safety FU		Efficacy (Imaging) FU Visits	Survival FU
Visit Timing/ Cycle No.													
Cycle Day		1	8	15	1	15	1	1	1	At DC	30 days after last dose	Q8W for 24 weeks, then Q12W	Q12W

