8 STUDY ASSESSMENTS AND PROCEDURES

- Study procedures and their timing are summarized in the SoA.
- Adherence to the study design requirements, including those specified in the SoA, is essential and required for study conduct.
- The investigator is responsible for ensuring that procedures are conducted by appropriately qualified (by education, training, and experience) staff. Delegation of study site personnel responsibilities will be documented in the Investigator Trial File Binder (or equivalent).
- All study-related medical or dental decisions must be made by an investigator who is a qualified physician.
- All screening evaluations must be completed and reviewed to confirm that potential participants meet all eligibility criteria. The investigator will maintain a screening log to record details of all participants screened and to confirm eligibility or record reasons for screening failure, as applicable.
- Procedures conducted as part of the participant's routine clinical management (eg, blood count) and obtained before signing of ICF may be utilized for screening or baseline purposes provided the procedure met the protocol-specified criteria and were performed within the time frame defined in the SoA.

- Additional evaluations/testing may be deemed necessary by the investigator and or the Sponsor for reasons related to participant safety. In some cases, such evaluation/testing may be potentially sensitive in nature (eg, HIV, Hepatitis C), and thus local regulations may require that additional informed consent, and assent if applicable, be obtained from the participant. In these cases, such evaluations/testing will be performed in accordance with those regulations.

The maximum amount of blood collected from each participant over the duration of the study will be provided in the laboratory manual. Refer to Appendix 7 for country-specific requirements.

Repeat or unscheduled samples may be taken for safety reasons or for technical issues with the samples.

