8.3.6.1 Hematology and Clinical Chemistry

Hematology (complete blood count with differential) and clinical chemistry will be performed within 7 days prior to the first dose of study intervention and do not need to be repeated at C1D1 (unless clinically indicated) and within 72 hours prior to all subsequent visits (Appendix 2). All clinical laboratory tests during the study will be performed by local laboratories. All hematology, blood chemistry (including pregnancy test, as applicable), and urinalysis samples are to be obtained prior to study drug administration and sent to the local laboratory on the day of collection, unless otherwise instructed.

All hematology, blood chemistry (including pregnancy test, as applicable), and urinalysis samples are to be obtained and assessed and the results reviewed prior to study drug

administration on C1D1 and within 72 hours prior to the visit for all subsequent cycles. If \geq Grade 3 hematologic or clinical chemistry toxicity, repeat laboratory test and AEs assessment at least every 3 days (until improvement to $<$ Grade 3). Refer to [Table 3](#) for the management of lenvatinib-related toxicity.

Electrolytes such as potassium, calcium, and magnesium should be monitored and abnormalities, when considered clinically significant, should be corrected in all participants before starting treatment.

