8.3.6.2 Urine Dipstick/Urinalysis

Urine dipstick (preferred method)/urinalysis testing during screening can be performed within 7 days prior to the first dose of lenvatinib (C1D1) as part of the screening visit and does not need to be repeated at C1D1 (unless clinically indicated) and within 72 hours prior to the visit at subsequent cycles.

Urine dipstick/urinalysis testing will be performed during screening and on Days 1 and 15 of Cycles 1 and 2, on Day 1 of every cycle thereafter or more frequently as clinically indicated, at EOT and at the Safety Follow-up visit (Section 1.3). For participants with proteinuria $\geq 2+$ (≥ 100 mg/dL), urine dipstick/urinalysis testing should be performed on Day 15 (or more frequently as clinically indicated) until the results have been 1+ or negative for 2 consecutive months. If a new event of proteinuria $\geq 2+$ (≥ 100 mg/dL) occurs, the participant must resume the Day 15 urine dipstick/urinalysis testing for evaluation of proteinuria until results are 1+ (≥ 10 mg/dL) or negative for 2 consecutive months. Participants who have $\geq 2+$ (≥ 100 mg/dL) proteinuria on dipstick urinalysis should perform a spot P/C test and if possible, undergo a 24-hour urine collection. Urine glucose should be performed as part of urine dipstick/urinalysis.

For participants with proteinuria $\geq 2+$ (≥ 100 mg/dL), see Section 6.6.3 for management of proteinuria.

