8.3.6.3 Thyroid Function Testing

The screening blood sample for thyroid function testing can be obtained within 7 days prior to the first dose of lenvatinib (C1D1) as part of the screening visit and does not need to be repeated at C1D1 (unless clinically indicated) and within 72 hours prior to all subsequent visits.

Thyroid function tests (TSH and free T4) should be assessed at Screening, C2D1, every 2 cycles thereafter, at EOT, and at the Safety Follow-up visit. Participants may be dosed while thyroid function test results are pending; however, the results must be reviewed by the investigator when available.

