8.11.1 Screening

Documented consent/assent must be obtained prior to performing any protocol-specific procedure. Results of a test performed prior to the participant signing consent as part of routine clinical management are acceptable in lieu of a screening test if performed within the specified time frame. Screening procedures are to be completed within 28 days prior to the first dose of study intervention except for the following:

- Laboratory tests are to be performed within 7 days prior to the first dose of study intervention. Exceptions are hepatitis testing and HIV testing which may be performed up to 28 days prior to the first dose of study intervention, if mandated by local health authority (see Appendix 7 for country-specific requirements).
- Evaluation of Lansky play score or KPS is to be performed within 7 days prior to the first dose of study intervention.
- For women of reproductive potential, a urine or serum pregnancy test will be performed within 24 hours prior to the first dose of study intervention. If urine pregnancy results cannot be confirmed as negative, a serum pregnancy test will be required (performed by the local study site laboratory).
- Providing archival tumor tissue is not required for participation in the study and is an optional collection. If an archival tumor tissue is available from a biopsy performed as standard of care prior to study treatment, it can be submitted to the central laboratory anytime during the study.

Participants may be rescreened after initially failing to meet the inclusion/exclusion criteria. Results from assessments during the initial screening period are acceptable in lieu of a repeat screening test if performed within the specified time frame and the corresponding inclusion/exclusion criteria is met. Participants who are rescreened will retain their original screening number.

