9.6.2 Statistical Methods for Safety Analyses

Safety and tolerability will be assessed by clinical review of all relevant parameters, including AEs, laboratory tests, and vital signs. Safety summaries will be pooled across all indications. The additional safety analyses for each tumor type might be conducted if desired and will be documented in the sSAP. The safety analysis population will be used for the analysis of safety data. TEAE is defined as all AEs from the treatment start date until 30 days after last dose (30 days for SAE). The incidence of TEAEs and SAEs will be summarized by system organ class and preferred term. Continuous measures such as changes from baseline in laboratory test data, vital signs, 12-lead ECGs, cardiac function by echocardiography or MUGA scan, urine dipstick, and Lansky play scores or KPS scores will be summarized using descriptive statistics (mean, standard deviation, etc.) for baseline, on-treatment, and change-from-baseline values.

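### Section 9.5.2 allows laboratory change from baseline only with a C1D1 pre-allocation value, but TSH and free T4 have no scheduled C1D1 sample, so as written their change summaries would be essentially empty

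*Combined protocol and SAP*

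**What the plan says.** Section 9.5.2, in a paragraph on laboratory and vital sign parameters, sets two conditions for analysis. At least one post-dose measurement is needed for a parameter to be analyzed, and for change from baseline: "To assess change from baseline, a baseline measurement at C1D1 prior to allocation is also required". It gives no screening alternative.

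Section 9.6.2 plans descriptive statistics at baseline, on treatment and as change from baseline, covering "Continuous measures such as changes from baseline in laboratory test data" and, among others, urine dipstick.

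The sampling schedule differs by test:

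- **Thyroid.** The Schedule of Activities (Section 1.3) says "TSH and free T4 should be assessed for all participants". Its row is marked at Screening and C2D1, with the C1D1 cell blank. Section 8.3.6.3 agrees: "Thyroid function tests (TSH and free T4) should be assessed at Screening, C2D1, every 2 cycles thereafter", then EOT and Safety Follow-up. Both places say the screening sample is not repeated at C1D1 unless clinically indicated.
- **Hematology and chemistry.** C1D1 is marked in the schedule, but Section 8.3.6.1 has these tests done "within 7 days prior to the first dose of study intervention and do not need to be repeated at C1D1 (unless clinically indicated").
- **Urine dipstick.** C1D1 is marked, with the same waiver in Section 8.3.6.2: the test can be done "as part of the screening visit and does not need to be repeated at C1D1 (unless clinically indicated").

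Section 8.11.1 adds: "Laboratory tests are to be performed within 7 days prior to the first dose of study intervention". Section 8 lets routine-care results "obtained before signing of ICF may be utilized for screening or baseline purposes" if they meet protocol criteria and the schedule's time frames.

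**The concern.** An inclusion rule for an analysis should be one that the trial's own visit schedule can satisfy. Here the rule asks for a value at a time point where thyroid tests are not scheduled, and where the other laboratory tests may be omitted. A programmer who follows Section 9.5.2 would set aside valid pre-dose screening values.

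Safety is a secondary objective, and clinical laboratory values are a named endpoint in Section 3. Section 2.2.1.2 lists hypothyroidism and proteinuria among the TEAEs seen in 40% or more of the earlier single-agent pediatric osteosarcoma cohort. Thyroid function is therefore an area where a change summary would be informative. The alternative is that the programmer quietly departs from the written rule, which a pre-specified plan is meant to prevent.

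**Working it through.** There is no stated figure to reproduce. The check compares the rule with the schedule.

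**1. Is the post-dose condition met for thyroid?** Section 4.1 estimates 12 cycles of treatment. Day 1 samples fall at C2, C4, C6, C8, C10 and C12, which is 6. Adding EOT and Safety Follow-up gives 6 + 2 = 8, or 7 if those two visits are combined as Section 8.11.4 allows. A participant who stops between C2D1 and C4D1 has up to 1 + 2 = 3. Post-dose data are not the obstacle.

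**2. Is the baseline condition met for thyroid?** Let N be the size of the Safety Analysis Set and p the share with a C1D1 pre-allocation thyroid value. The number eligible for change from baseline is at most N × p.

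- From the schedule alone p = 0, so the number is 0 for any N.
- The only sources of p > 0 are a clinically indicated C1D1 test or a screening sample drawn on C1D1 before allocation. The documents do not give that share. Assuming p between 0% and 10%: for N = 36, 0 to 3.6, or about 4; for N = 150, 0 to 15.
- These N are illustrative. The 36 is the planned minimum of 9 evaluable participants in each of 4 cohorts; the Safety Analysis Set is everyone dosed, including dosed participants who were replaced as not evaluable. The 150 is the approximate upper estimate of enrollment.
- If the last pre-dose value counted, every participant with a screening value and at least one post-dose value would qualify.

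**3. Could C1D1 prior to allocation simply mean screening?** Sections 8.3.6.4 (performance score) and 8.3.6.6 (pregnancy test) list the two as separate time points. Where the schedule lets one stand for the other (performance scores, hematology and chemistry), it lets a C1D1 result serve as the screening value for eligibility. No text lets a screening value serve as the C1D1 value in the analysis.

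**4. Which other parameters are exposed?** Counting Table 7 without INR/PT, microscopy and the pregnancy test: hematology 10 + chemistry 20 + dipstick 3 = 33. Two chemistry tests are conditional under the table notes: CO2/bicarbonate only where local standard of care, and direct bilirubin only if total bilirubin is elevated. That leaves 33 − 2 = 31 unconditionally scheduled parameters whose C1D1 sample may be waived. The 7-day window in Section 8.11.1 is the same as the waiver's, so anyone screened on schedule could use it. The share who would is not given.

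**5. Relevance.** 0.40 × 31 = 12.4, so at least 13 of the 31 earlier participants had hypothyroidism, and at least 13 had proteinuria (12 of 31 would be 38.7%).

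Vital signs are scheduled at C1D1 and are not part of this point.

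**The case against.** The strongest reply is that the intent is plain. Section 8 accepts routine-care results for baseline purposes, and saying that a sample need not be repeated at C1D1 suggests the screening sample fills that slot. An analyst would probably use the last pre-dose value, and a supplemental SAP, not among the documents, may say so. This is a fair guess at intent, but Section 8 is a general permission and does not lift the specific condition in Section 9.5.2. On whether a pre-C1D1 laboratory value can be a baseline, the two sections give different answers.

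Several limits do stand, and they rule out stronger readings that a reader might infer:

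- **That the thyroid summaries would be wholly empty.** Clinically indicated C1D1 tests, or screening draws on C1D1 before allocation, could supply a few baselines.
- **That a count such as 0 of 36 describes the loss.** The 36 is a floor for evaluable participants, not the size of the Safety Analysis Set.
- **That hematology, chemistry and dipstick data would be lost to a known extent.** The schedule lets hematology and chemistry results obtained on C1D1 before allocation serve as screening values, so sites may well sample then. The loss is possible but unquantified.
- **That thyroid or renal toxicity would be missed.** TEAE incidence does not depend on this rule, and Section 6.6.3 grades proteinuria by protein-creatinine ratio or 24-hour protein, not by dipstick change.

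**Conclusion.** The rule is wrong as written for thyroid tests: it cannot be met from scheduled sampling. TSH and free T4 would have no scheduled qualifying baseline in any participant, so their change-from-baseline summaries would be essentially empty. If baseline in Section 9.6.2 is also taken to mean C1D1, the thyroid baseline summary would be essentially empty too. For the 31 unconditionally scheduled hematology, chemistry and dipstick parameters, and the two conditional ones when done, an unknown share of participants could be dropped.

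This rests on applying Section 9.5.2 literally and on no other document redefining baseline. The effect is confined to descriptive safety summaries. ORR, TEAE incidence and on-treatment summaries are untouched, and no data are lost, because the screening values are collected. It is worth correcting before database lock but does not bear on the trial's main conclusions.

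**What to change.** Replace the Section 9.5.2 sentence with: *Baseline is the last non-missing measurement taken before the first dose of lenvatinib, including screening values.* Apply the same definition to all change-from-baseline safety measures in Section 9.6.2. For ECG this makes the screening reading the baseline, because the schedule places the C1D1 ECG about 2 hours after the dose. A pre-dose C1D1 laboratory value, where one exists, remains the baseline. It would help to add that routine-care results accepted for screening under Section 8 count as screening values.

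The cost is one sentence, with no new assessments. Section 9 already provides for changes to non-confirmatory analyses to be documented in the supplemental SAP and referenced in the study report.
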